3.1 Primary Endpoint

Primary Safety and Performance Endpoint

This study has a combined Safety and Performance endpoint derived from the Dialysis Outcomes and Practice Patterns Study (DOPPS) data. The combined Primary Endpoint will be overall complications including infectious and non-infectious complications at 3 months.

Infectious Complications are defined as:

Complications due to any documented diagnosis of access infection requiring medical intervention (managed in an outpatient or inpatient setting) or sepsis as diagnosis in the hospitalization file whether access related or not.⁴

Non-infectious complications are defined as:

Complication due to any noninfectious cause (thrombosis of the access, fibrin material within or around a catheter, catheter migration, central vein stenosis or thrombosis) requiring a revision procedure to maintain patency or improve access performance (i.e., thrombolysis, angioplasty, or surgical correction) in an inpatient or outpatient setting or removal or abandonment with creation of a new access that was not due to an access-related infection).⁴

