4.2 Scientific Rationale for Study Design

The combined safety and performance primary endpoint is compared to a performance goal of 31.5 complications per 1000 catheter days derived from the Dialysis Outcomes and Practice Patterns Study (DOPPS).⁵ The DOPPS data was chosen due to it's significant sample size of tunneled catheters (n=4207) and it's clear definition of non-infectious and infectious complications. DOPPS I-III enrolled 27, 129 participants that provided access data. DOPPS I enrolled within France, Germany, Italy, Japan, Spain, the United Kingdom, and the United States. DOPPS II and DOPPS III enrolled in Australia, Belgium, Canada, New Zealand, and Sweden.⁵ There have been few hemodialysis catheter studies performed in the last 10 years with many lacking sufficient sample size for statistically powered endpoints. The hemodialysis catheter studies that report 'complication' rates or infection rates have a significant variance in definitions. The KDOQI guidelines have stated a need for consistent definitions and outcomes between tunneled catheter studies.⁶ DOPPS is a globally renowned study providing clinically meaningful definitions with a significant sample size not seen in other studies.

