The primary endpoint for this study is a combined complication rate of non-infectious and infectious complications. Non-infectious complications are defined as, complications due to any noninfectious cause (thrombosis of the access, fibrin material within or around a catheter, catheter migration, central vein stenosis or thrombosis) requiring a revision procedure to maintain patency or improve access performance (i.e., thrombolysis, angioplasty, or surgical correction) in an inpatient or outpatient setting or removal or abandonment with creation of a new access that was not due to an access-related infection). This definition of non-infectious provides the clinically relevant point of re-intervention. Thrombosis, fibrin material, and catheter migration are all common events for tunneled catheters. When these events start to disrupt dialysis treatment, they require re-intervention thus putting more burden on the patient and healthcare system. The other part is infectious complications defined as, complications due to any documented diagnosis of access infection requiring medical intervention (managed in an outpatient or inpatient setting) or sepsis as diagnosis in the hospitalization file whether access related or not. Infection rate for catheters is arguably the most crucial reported value being the main cause of catheter related deaths. The infectious complications defined include exit site infections and all blood stream infections causing sepsis.

Showing a statistically significant difference by our powered primary endpoint against the performance goal will attest to the performance, safety, and clinical benefits of the Pristine™ Catheter.

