9.3 Relationship of Adverse Event to Device(s)/Procedure

Each AE will be assessed for its relationship to the study device or procedure according to the following guidelines.

- A. Assess each AE for its relationship to the device or procedure.
 - Device Related: This category should be restricted to AEs directly attributable to the study device used from the placement procedure of the Pristine™ Catheter to completion of all follow-up for that patient.
 - Procedure Related: A procedure includes any study-related activity performed during the index procedure of the Pristine™ Catheter.
- B. The following categories shall be used for assigning the certainty of the relatedness.

Table 3: Relationship of Adverse Events

Relatedness	Description
Not Related	Event is independent of study intervention and/or evidence exists that the event is related to another etiology. There must be an alternative etiology documented by the clinician.
Unlikely Related	Event in which the temporal relationship to study intervention makes a causal relationship improbable (e.g., the event did not occur within a reasonable time of the study device use) and in which underlying disease provides plausible explanations (e.g., the participant's clinical condition other concomitant treatments).
Likely Related	Event in which there is evidence to suggest a causal relationship and the influence of other factors is less likely. The event occurs within a reasonable time after use of the study device and is less likely to be attributed to concurrent disease.
Related	Event in which there is clear evidence to suggest a causal relationship and other possible contributing factors can be ruled out. The event occurs in a plausible time relationship to use of the study device and cannot be explained by concurrent disease.

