Possibly Related AE	An AE is possibly related if it is capable of being related but relatively unlikely or there is insufficient information to determine if the AE is related to the device or procedure.
Post Procedure Event	AE that occurred after the index procedure.
Principal Investigator	Qualified person responsible for conducting the clinical investigation at an investigation site. If a clinical investigation is conducted by a team of individuals at an investigation site, the PI is responsible for leading the team.
Procedure access Site	A site of incision access during index procedure.
Procedural Event	AE that occurred during the index procedure.
Procedure Duration	The duration of the index procedure as defined in this CIP.
Procedure Related AE	AEs directly attributable to the index procedure.
Procedure Success	Successful catheter creation using the Pristine™ Long-Term Hemodialysis Catheter with flow confirmed through the catheter.
Recruitment	Active efforts to identify participants who can be suitable for enrolment into the clinical investigation.
Re-interventions	Any additional procedures with the initial catheter after the index procedure.
Screen Failure	A participant who is excluded from this clinical investigation as based on the eligibility criteria.
Serious Adverse Device Effect (SADE)	ADE that has resulted in any of the consequences characteristic of a SAE.

Term	Definition
Serious Adverse Event	
An AE that led to any of the following:
 
 • Death; or • Serious deterioration in the health of the participant, users or other persons as defined by one or more of the following: 
 - A life-threatening illness or injury; or - A permanent impairment of a body structure or a body function including chronic diseases; or - In-patient or prolonged existing hospitalization; or - Medical or surgical intervention to prevent life-threatening illness or injury or permanent impairment to a body structure or a body function; or • Fetal distress, fetal death or a congenital abnormality or birth defect including physical or mental impairment. 
Note: Planned hospital visits and / or hospital stays, or procedures required by this CIP (including subsequent interventions assessed in the clinical investigation endpoints), without serious deterioration in health should not be considered SAEs.

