#### Infectious Complications

Complications due to any documented diagnosis of access infection requiring medical intervention (managed in an outpatient or inpatient setting) or sepsis as diagnosis in the hospitalization file whether access related or not.

Subject will be considered as having an infectious complication and will be counted as an event if the subject has experienced a device-related infection prior to the subject's end day of investigation period:

- **AE CRF Page:** Start Date of AE ≤ End Day of Investigation period **AND** Relationship to study Device: Equals 'Related' or 'Likely Related' **AND** Was event infectious: Equals Yes; subject will be considered as a failure at AE start date

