#### Non-infectious complications

Complication due to any noninfectious cause (thrombosis of the access, fibrin material within or around a catheter, catheter migration, central vein stenosis or thrombosis) requiring a revision procedure to maintain patency or improve access performance (i.e., thrombolysis, angioplasty, or surgical correction) in an inpatient or outpatient setting or removal or abandonment with creation of a new access that was not due to an access-related infection.

Subject will be considered as having a non-infectious complication and will be counted as an event if the subject has experienced a device-related non-infectious AE resulting in a re-intervention prior to the subject's end day of investigation period:

- **AE CRF Page:** Start Date of AE  $\leq$  End Day of Investigation period **AND** Relationship to study Device: Equals 'Related' or 'Likely Related' **AND** Was event infectious: Equals No **AND** Did AE Result in a Catheter Re-Intervention: Equals Yes; subject will be considered as a failure at AE start date

For each subject, the number of complications through the investigational duration is estimated as:

$$((\text{Number of observed infectious complications} + \text{Number of observed non-infectious complications}) * 1000) / \text{Length of investigation duration (Days)}$$

Length of investigation duration (Days) is from the date of index procedure to the end day of each subject's investigation period (End day of investigation period – Date of index procedure + 1); the end day of investigational period will be the earliest occurrence date of the following three events:

- If a subject's Pristine™ Catheter is removed due to Kidney Transplant, Transferred to AVG/AVF, Peritoneal Dialysis, Withdrawal of Care, or Other reasons, then the date of removal will be used to calculate the length of investigation duration. That is:
  - **Hemodialysis Catheter Re-Interventions CRF page:** Catheter removal Equals Yes **AND** Reason for catheter removal Equals: Kidney Transplant, Transferred to AVG/AVF, Peritoneal Dialysis, Withdrawal of Care, or Other; date of re-intervention is used in the estimation of investigation duration

$$\text{Length of investigation duration (Days)} = \text{Removal date} - \text{date of index procedure} + 1$$

- If a subject discontinues early, then the discontinuation date will be used to calculate the length of investigation duration.
 

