### **5.3.2 Rate of freedom from Device and/or Procedure-related adverse events, at 1-month, 3-months, 6-months, and 12-months post-index procedure.**

#### **Binary Analysis**

Subject will be considered as having device and/or procedure-related adverse events for a given visit if the subject has experienced device and/or procedure-related adverse events prior to the upper limit of visit window for the visit:

- **AE CRF Page:** AE start date <= upper limit of the visit window AND (Relationship to Device: Is 'Related' or 'Likely Related' OR Relationship to Procedure: Is 'Related' or 'Likely Related') ; subject will be considered as a failure at the AE date

If the subject has not become failure and experience one of the following events prior to the lower limit of visit window, then subject will be considered as non-evaluable at the earliest occurrence of following event dates.

- Catheter has been removed due to Kidney Transplant, Transferred to AVG/AVF, Peritoneal Dialysis, Withdrawal of Care, or Other reasons
  - **Hemodialysis Catheter Re-Interventions CRF page:** *Catheter removal Equals Yes AND Reason for catheter removal Equals: Kidney Transplant, Transferred to AVG/AVF, Peritoneal Dialysis, Withdrawal of Care, or Other*

OR

- Subject has discontinued from the study.

If the subject has experienced any of the above non-evaluable events prior to the lower limit of visit window subject will be counted as a non-evaluable for a given visit. Else subject will be considered as a success (freedom from device and/or procedure-related adverse events) for a given visit.

The rate of freedom from device and/or procedure-related adverse events will be reported with 95% confidence interval from the exact binomial method. The analysis will be performed on the ITT population through 1-month, and mITT population through 1-month, 3-months, 6-months, and 12-months.

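### SAP 5.2.1 counts a primary-endpoint complication only if it is coded device-related, a condition the endpoint definition does not contain

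*SAP*

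**What the plan says.** Protocol 3.1 defines infectious complications as access infections that need medical intervention, plus "sepsis as diagnosis in the hospitalization file whether access related or not". Non-infectious complications are those of any non-infectious cause (access thrombosis, fibrin, migration, central vein stenosis or thrombosis are listed) that need a revision procedure, or that lead to removal or abandonment with a new access. Protocol 4.2 adds: "The infectious complications defined include exit site infections and all blood stream infections causing sepsis". Protocol 10.5, Protocol Appendix A and SAP 2.7.1 contain no relatedness condition either.

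SAP 5.2.1 restates both definitions and then gives the programming rules. An infectious complication is "counted as an event if the subject has experienced a device-related infection", with the AE-page field for relationship to the device coded Related or Likely Related. A non-infectious complication is counted if the subject has "experienced a device-related non-infectious AE resulting in a re-intervention", under the same coding.

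On relatedness, Protocol 9.3 says of the device-related class: "This category should be restricted to AEs directly attributable to the study device". It gives procedure-relatedness a class of its own. For a secondary endpoint, SAP 5.3.2 accepts either code ("OR Relationship to Procedure: Is 'Related' or 'Likely Related").

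The benchmark is 31.5 complications per 1000 patient-days, which becomes 36.5 with a margin of 5. Protocol 4.2 says the source study was chosen partly for its "clear definition of non-infectious and infectious complications".

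**The concern.** The definition and the counting rule sit next to each other in one SAP section and disagree. A hospitalization for sepsis coded not device-related meets the first and fails the second. An access infection or migration coded to the procedure alone is dropped as well. The exposure in the denominator is unchanged, so each dropped event lowers the observed rate.

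In a single-arm trial against a fixed goal, the comparison is only as good as the match between how events are counted here and how they were counted for the benchmark. The study is unblinded (SAP 2.3). Protocol 9.3 does not name who judges relatedness, no adjudication is described, and the Medical Monitor's stated task (Protocol 9.5.1) is trend review and signal detection. An unadjudicated code therefore decides the primary numerator. Nothing in either document justifies the condition, adjusts the goal for it, or plans an analysis without it. The only planned sensitivity analysis is per-protocol.

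At stake are the non-inferiority claim, the superiority claim conditional on it, and the rate itself, which Protocol 3 says is intended for the labeling.

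**Working it through.** **Inputs.** From Protocol 10.2 and SAP 2.4: one-sided alpha 0.025; performance goal 36.5 and expected rate 31.5 per 1000 days; 12,765 patient-days; 15% attrition; 80% power for non-inferiority and 85% for superiority (26.5 against 31.5). The share of qualifying events lost, f, is not in the documents and is an assumption here.

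**Reproducing the plan.** Evaluable exposure is T = 12,765 × 0.85 = 10,850 days. With an exact Poisson test, the critical count c is the largest value with P(X ≤ c | 0.0365 × T = 396.0) < 0.025.
- c = 357, which is 357/10,850 = 32.9 per 1000 days; size 0.0250.
- Power at a true 31.5 (341.8 expected events) is 80.3%.
- For superiority to 31.5, c = 305 and power at 26.5 is 85.5%.

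These match the stated 80% and 85%, so 12,765 is the attrition-inflated exposure.

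**Effect of a net loss f.** If the true rate under the protocol definition is r per 1000 days, the filtered count has mean r(1 − f)T/1000. The chance of declaring non-inferiority is P(X ≤ 357) at that mean:

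| True rate r | f = 0 | 2% | 5% | 10% | 20% |
|---|---|---|---|---|---|
| 36.5 | 2.5% | 5.9% | 16.7% | 52.6% | 98.8% |
| 38 | 0.3% | 0.9% | 4.1% | 24.2% | 93.5% |
| 40 | <0.1% | <0.1% | 0.3% | 4.5% | 71.2% |

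At r = 36.5 the four losses are about 8, 20, 40 and 79 of 396 events. If all 12,765 days accrue (critical count 423), the first row for f = 2% to 20% becomes 5.9%, 18.2%, 58.4% and 99.5%.

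The margin is 5/36.5 = 13.7% of the goal. Losing that share makes a device exactly at the goal look like 31.5, and it then passes 80% of the time.

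**Superiority.** Taking the protocol's superiority goal of 31.5 and a true rate of 31.5, P(X ≤ 305) is 2.3% with no loss, and 14.3%, 45.6% and 97.2% for f = 5%, 10% and 20%.

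**Departures that add events.** The infectious rule requires neither medical intervention nor that the infection be of the access or be sepsis. The non-infectious rule accepts any re-intervention, which Protocol Appendix A defines as "Any additional procedures with the initial catheter after the index procedure". Both can bring in events outside the definition, so f must be read as a net share, and the text does not fix its size or guarantee its sign.

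**Analysis set.** Protocol 10.3 and 10.5 use ITT (catheter placed). SAP 5.2.1 and 5.2.2 use mITT, which omits participants with a catheter inserted but no first dialysis session. The SAP's own ITT is wider than the protocol's, since it includes participants with no device inserted. If 3 participants with one event each were omitted from 396 events in 10,850 days:
- 10 days each: 393/10,820 = 36.3 per 1000 (−0.2)
- 60 days each: 393/10,670 = 36.8 per 1000 (+0.3)
- Break-even: 1000/36.5 = 27.4 days each

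This effect is small and its direction is not established.

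**The case against.** The literal conflict is confined to sepsis. For non-infectious events the definition lists access or catheter causes, and the filter is an added condition more than a contradiction. Thrombosis, fibrin or migration would often be coded device-related. Protocol 9.3 allows the Not Related code only with a documented alternative cause, and Protocol 9.1.3 counts events from implantation, operation and user error as device effects. The loss may therefore be small, and the wider parts of the rules may offset it.

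The false-pass figures also apply only near the goal. At the plan's own 31.5, non-inferiority is true and the filter cannot create a false claim of it. The feasibility study points lower still. Take all 19 reported adverse events (9 + 2 + 2 + 6) plus about 4 patency losses among 44 catheters, over an assumed mean follow-up of 60 to 180 days. The rate is 23/(44 × 60) to 23/(44 × 180), or 8.7 to 2.9 per 1000 days, which is about 95 to 31 events in 10,850 days against a pass limit of 357. Finally, what the 31.5 counted cannot be checked from the documents, and the protocol's reference numbers for the benchmark definition vary between sections.

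Most of this stands as a limit on size. The feasibility data come from one non-US site that also took acute renal failure, so they are indicative only. None of it removes the mismatch: the rule is not the protocol's endpoint, and if it errs in both directions it still does not measure that endpoint. At a true 31.5 the exposed claim is superiority, as calculated above. The protocol's own statements tie the goal to the unfiltered definition, and nothing in the documents ties it to a device-related one.

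**Conclusion.** The concern holds and must be fixed. SAP 5.2.1 imposes a device-relatedness condition that the primary endpoint lacks and that, for sepsis, its definition expressly excludes. The filtered rate is not like for like with the goal of 36.5.

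The contradiction is certain from the text; its numerical effect is not. At the boundary, an assumed net loss of 5% raises the false non-inferiority rate from 2.5% to about 17%, and 10% raises it to about 53%. These figures assume Poisson counts, 10,850 evaluable days and a net loss after any offsetting additions. They fall quickly as the true rate moves above the goal. If the true rate is well below the goal, the harm is to the reported rate, which would be too low by the net share lost, and not to the pass or fail decision. The analysis-set mismatch is real but minor.

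**What to change.** Replace both counting rules in SAP 5.2.1 with rules that match Protocol 3.1 and apply whatever the device or procedure relatedness code:

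- (a) access infections requiring medical intervention;
- (b) any sepsis diagnosis in the hospitalization file;
- (c) non-infectious events leading to a revision procedure for patency or access performance, or to removal or abandonment with a new access not caused by access infection.

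State how an episode meeting both (a) and (b) is counted. Do not simply delete the relatedness condition: the infectious flag alone would then admit infections such as pneumonia that do not qualify. Keep the device-related count as a supportive analysis. The alternative, a goal re-derived for device-related events only, would need benchmark data that the documents do not give.

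Make the protocol's ITT (catheter placed) the primary set, using each participant's available exposure (Protocol 7.4.1 limits collection to 30 days for some), with mITT as a sensitivity analysis.

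The cost is revised wording in SAP 5.2.1 and the derived-data specification (SAP Appendix 2). The SAP refers to fields for infection type and removal reason, but to none for hospital-file sepsis or for medical intervention. The CRFs are not in the documents, so confirm that these events can be identified; review of AE terms or site queries may be needed. The observed rate may come out less favourable.

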#### Non-infectious complications

Complication due to any noninfectious cause (thrombosis of the access, fibrin material within or around a catheter, catheter migration, central vein stenosis or thrombosis) requiring a revision procedure to maintain patency or improve access performance (i.e., thrombolysis, angioplasty, or surgical correction) in an inpatient or outpatient setting or removal or abandonment with creation of a new access that was not due to an access-related infection.

Subject will be considered as having a non-infectious complication and will be counted as an event if the subject has experienced a device-related non-infectious AE resulting in a re-intervention prior to the subject's end day of investigation period:

- **AE CRF Page:** Start Date of AE  $\leq$  End Day of Investigation period **AND** Relationship to study Device: Equals 'Related' or 'Likely Related' **AND** Was event infectious: Equals No **AND** Did AE Result in a Catheter Re-Intervention: Equals Yes; subject will be considered as a failure at AE start date

For each subject, the number of complications through the investigational duration is estimated as:

$$((\text{Number of observed infectious complications} + \text{Number of observed non-infectious complications}) * 1000) / \text{Length of investigation duration (Days)}$$

Length of investigation duration (Days) is from the date of index procedure to the end day of each subject's investigation period (End day of investigation period – Date of index procedure + 1); the end day of investigational period will be the earliest occurrence date of the following three events:

- If a subject's Pristine™ Catheter is removed due to Kidney Transplant, Transferred to AVG/AVF, Peritoneal Dialysis, Withdrawal of Care, or Other reasons, then the date of removal will be used to calculate the length of investigation duration. That is:
  - **Hemodialysis Catheter Re-Interventions CRF page:** Catheter removal Equals Yes **AND** Reason for catheter removal Equals: Kidney Transplant, Transferred to AVG/AVF, Peritoneal Dialysis, Withdrawal of Care, or Other; date of re-intervention is used in the estimation of investigation duration

$$\text{Length of investigation duration (Days)} = \text{Removal date} - \text{date of index procedure} + 1$$

- If a subject discontinues early, then the discontinuation date will be used to calculate the length of investigation duration.
 
$$\text{Length of investigation duration (Days)} = \text{Discontinuation Date} - \text{Date of index procedure} + 1$$
- If the subject has not experienced any of the above events prior to the 3-months visit date, then the 3 months visit date will be used to calculate the length of investigation duration; in case of subject having the 3 months visit out of window and after day 105 or the subject misses the 3 months visit, then day 105 will be the end date of investigational period.
 
$$\text{Length of investigation duration (Days)} = \min((3 \text{ months visit date} - \text{date of index procedure} + 1), 105 \text{ days})$$

The analysis will be performed on the mITT population and repeated with per-protocol population as sensitivity analyses.

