10.5 Primary Endpoint

The combined primary endpoint is the overall rate of infectious complications and non-infectious complications requiring revision to maintain patency and improve access performance at 3 months. Based on the DOPPS study data, competitor control devices had an average incidence rate of 31.5 complications per 1000 patient days. To show non-inferiority of the Pristine™ Catheter, a 5 complications per 1000 patient days non-inferiority margin is used to establish a performance goal (PG) of 36.5 events per 1000 patient days.

The analysis of the primary endpoint will be based on the following test of Poisson rate:

H₀: The complication rate through 3 month is greater than or equal to 36.5 events per 1000 patients days at 3 months.

H₁: The complication rate through 3 month is less than 36.5 events per 1000 patient days at 3 months.

That is:

$$\mathbf{H_0: \lambda \geq \lambda_0}$$

$$\mathbf{H_1: \lambda < \lambda_0}$$

Where λ_0 is the PG of 36.5 events per 1000 patient days.

A one-sided p-value will be derived based on an Poisson distribution. The Pristine™ Catheter will be considered to have achieved the primary endpoint objective if the one-sided p-value is less than 0.025.

Conditioned on the success of the above test, a superiority test will be conducted to show that the Pristine™ Catheter is superior to the performance goal. The above test will be repeated with a PG of 31.5 events per 1000 patient days.

The analyses of the primary endpoint will be based on the ITT population and repeated with per-protocol population as sensitivity analyses.

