### Based on hypothesis test of Non-inferiority

- Assumptions:
  - The complication rate of our performance goal is estimated at 31.5 events per 1000 patient days with a 90 days follow-up based on DOPPS study data. The complication rate for Pristine is expected to be similar.
  - The performance goal is set at 36.5 events per 1000 days using a 5 events per 1000 days non-inferiority margin.
  - The attrition through 90 days is assumed to be 15%.
  - The Type 1 error is 0.025 (one-sided).
  - The Type 2 error is 0.2.
- Sample Size:
  - Total required exposure is 12765 patient days which translates to 142 participants with average exposure of 90 days (PASS 2019).

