### 5.2.2 Hypothesis Testing

The primary endpoint is the overall rate of infectious complications and noninfectious complications requiring revision to maintain patency and improve access performance at 3 months. Based on the DOPPS study data, competitor control devices had an average incidence rate of 31.5 complications per 1000 patient days. To show noninferiority of the Pristine™ Catheter, a 5 complications per 1000 patient days non-inferiority margin is used to establish a performance goal (PG) of 36.5 events per 1000 patient days.

The Primary Patency endpoint will be evaluated by the following hypothesis:

$H_0$ : The complication rate through 3 month is greater than or equal to 36.5 events per 1000 patients days at 3 months.

$H_1$ : The complication rate through 3 month is less than 36.5 events per 1000 patient days at 3 months.

That is:

$H_0: \lambda \geq \lambda_0$

$H_1: \lambda < \lambda_0$

Where  $\lambda_0$  is the PG of 36.5 events per 1000 patient days.

A one-sided p-value will be derived based on a Poisson distribution. The Pristine™ Catheter will be considered to have achieved the primary endpoint objective if the one-sided p-value is less than 0.025.

Conditioned on the success of the above test, a superiority test will be conducted to show that the Pristine™ Catheter is superior to the performance goal. The above test will be repeated with a PG of 26.5 events per 1000 patient days.

The analyses of the primary endpoint will be based on the mITT population and repeated with per-protocol population as sensitivity analyses. The analyses will be conducted after the last active treated subject completes their 3-month follow-up. The number of complications per 1000 patient days will be estimated by Poisson regression model with only the intercept term, and the estimate and 95% CI will be provided using the Wald method, and the p-value comparing to the PG will be calculated by a Chi-square test.

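### SAP 5.2.1 does not settle whether repeat complications in one subject count; if its subject-level rule is programmed literally, the 36.5 and 31.5 tests are passed at planned exposure whatever the device does

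*SAP*

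**What the plan says.** SAP 5.2.1 gives one data rule for each complication type. For infections, the subject "will be counted as an event if the subject has experienced a device-related infection" before the end of that subject's investigation period. For the other type, the subject "will be counted as an event if the subject has experienced a device-related non-infectious AE resulting in a re-intervention". Both rules close by assigning the subject a failure date: "subject will be considered as a failure at AE start date".

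The same section then defines a per-subject quantity, introduced as "For each subject, the number of complications through the investigational duration is estimated as". Its numerator adds "Number of observed infectious complications" to the matching non-infectious number, and its denominator is the subject's days in the investigation period. SAP 5.2.2 continues: "The number of complications per 1000 patient days will be estimated by Poisson regression model with only the intercept term".

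The goals are rates of complications. Protocol 10.5 states that "competitor control devices had an average incidence rate of 31.5 complications per 1000 patient days". SAP 2.4 adds the margin: "The performance goal is set at 36.5 events per 1000 days using a 5 events per 1000 days non-inferiority margin". For the superiority step, Protocol 10.5 uses 31.5 as the goal and SAP 5.2.2 uses 26.5.

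**The concern.** The data rules mark a subject as having had a complication of a given type or not, and attach one failure date. The SAP uses the same failure-date language in its binary and Kaplan-Meier secondary analyses, where one event per subject is intended. The primary test needs something else: a count in which one subject can contribute several events. Over 90 days the goals correspond to about three events per subject, which a rule allowing at most two cannot reach.

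Two competent programmers could therefore derive different primary results from the same data. Under one derivation, at about the planned exposure, the non-inferiority result would say nothing about the catheter. The study is single-arm and unblinded, and SAP 1.2 says that its results are intended for the device's labeling, so the counting rule should not be left to a programming choice.

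**Working it through.** **Inputs.** From SAP 2.4: goal 36.5 per 1000 days, assumed rates 31.5 (non-inferiority) and 26.5 (superiority), one-sided alpha 0.025, type 2 error 0.2, attrition 15%, 12,765 patient days, 142 participants, 90 days average. Superiority goals: 31.5 (Protocol 10.5) and 26.5 (SAP 5.2.2). From SAP 5.2.1: exposure ends at removal for listed reasons, at discontinuation or at the 3-month visit, and no later than day 105. The visit window opens at about day 75 (SAP 2.6, ±15 days).

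**1. The plan's own figure.** An exact one-sample Poisson test at 10,850 days rejects 36.5 at 357 events or fewer and has 80.3% power at a true rate of 31.5. For 31.5 against 26.5 the power is 85.5%. Then 10,850 / 0.85 = 12,765 days, and 12,765 / 90 = 141.8, so 142 participants. The stated exposure, sample size and 80% / 85% power all reproduce. So 12,765 days already includes the attrition allowance, and 10,850 days is what the plan expects to observe.

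**2. Events per subject that the goals imply over 90 days.**
- 36.5 × 90 / 1000 = 3.29
- 31.5 × 90 / 1000 = 2.84
- 26.5 × 90 / 1000 = 2.39

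All exceed 2, the literal maximum.

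**3. Cap under the literal rule.** Maximum rate = 2 × 1000 / mean exposure in days. With 142 subjects the maximum count is 284.
- Mean 105 days: 19.0 per 1000
- Mean 90 days: 22.2
- Mean 83.25 days: 24.0 (assumption: the 15% who drop out contribute half their time, 0.85 × 90 + 0.15 × 45)
- Mean 76.4 days (10,850 / 142): 26.2
- Mean 75 days: 26.7

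**4. Test result at the cap.** Exact one-sided p = P(X ≤ 284) for X Poisson with mean goal × total days. The largest passing count is in brackets.

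| Total days | Goal 36.5 | Goal 31.5 | Goal 26.5 |
|---|---|---|---|
| 12,780 (142 × 90) | 5e-20 (424) | 3e-10 (363) | 0.0013 (302) |
| 10,850 | 2e-9 (357) | 0.0007 (305) | 0.43 (254) |

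At a mean of 83.25 days the p-value against 26.5 is 0.050, also not a pass. A Wald test from an intercept-only Poisson model, the form that SAP 5.2.2 describes, gives the same decisions in all these cases.

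**5. Mean exposure above which the cap itself passes.** About 61.5 days for 36.5, 71 days for 31.5 and 85 days for 26.5.

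**6. Illustration below the cap.** Assume independent Poisson counts, 90 days per subject, and an infectious share f between 10% and 50%; the documents give no such share. With m events expected per subject, the capped mean is (1 − exp(−f·m)) + (1 − exp(−(1 − f)·m)). A true rate of 36.5 (m = 3.285) would be reported as 13.6 to 17.9 per 1000. A true rate of 100 (m = 9) would be reported as 17.7 to 22.0.

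**The case against.** The best defence is that the SAP means a recurrent count and the subject-level phrasing was carried over from the secondary endpoints. Much of this stands. Adding numbers of observed complications is an odd description of two yes/no flags, and a Poisson rate per patient day fits a count. Elsewhere the SAP labels binary analyses as such and refers to a first event when it means one; SAP 5.2.1 does neither. The data bullets can also be read as criteria for whether an adverse-event record qualifies. The count reading is at least as natural as the literal one. But nothing ranks the formula above the rules that supply its inputs, and no sentence says that repeats count. SAP Appendix 2 (derived data specification) may do so; it is listed, but its content is not in the documents supplied.

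A reader might go further and infer that the primary test cannot fail and that every goal is met automatically, with the rate held to about 22. The documents do not support that. The cap moves with exposure, which early removal, discontinuation and visits from about day 75 all shorten. At the plan's own post-attrition exposure the SAP's 26.5 goal is not met at the cap (p = 0.43), and even the 36.5 test fails there if mean exposure drops below about 61.5 days.

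A reader might also object that patient time keeps running after an event. That is correct for a recurrent-event rate, and it is further evidence that a count of all events is intended.

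**Conclusion.** The concern holds as an internal inconsistency in the primary endpoint's counting rule, not as proof that the SAP intends at most two events per subject. It is more than missing detail, because a stated rule conflicts with the estimator and with the sample-size basis.

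Its size depends on the literal reading being programmed. In that case the 36.5 test, which is the acceptance criterion in SAP 2.8, and the protocol's 31.5 superiority test are passed at both 12,780 and 10,850 days even if every subject has both complication types. Those two results would be uninformative at roughly planned exposure. The SAP's 26.5 goal is affected in the same way only at a mean of about 85 days or more. If all events are counted, this problem disappears and the plan's power figures apply as stated.

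The calculation assumes 142 analysed subjects, each able to contribute one event of each type, including those who leave early.

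**What to change.** In SAP 5.2.1, replace the subject-level wording in both the infectious and non-infectious rules with:

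> Every qualifying complication from the index procedure to the end of the investigation period is counted; a subject may contribute more than one; records of the same episode are counted once.

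Delete "subject will be considered as a failure at AE start date" from both rules in this section; it can stay in the secondary endpoints, where one event per subject is meant. Define in the derived data specification when two records belong to one episode, if it does not already do so. Leave the exposure rule running past each event.

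The cost is one SAP wording change and one derivation rule, made before the 3-month analysis. No new data field, extra participant or change to the goals is needed for this point. Stating that the Poisson model uses the per-subject count with log days as offset would be a useful but separate clarification.
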